9.6.4 Analysis of additional Secondary outcomes

The incidence rate of STI will be compared between SOC and ALERT- iTAB intervention arms using Fisher's exact test as will the rate of HIV seroconversion between groups (the rate of new HIV is expected to be low). In order to evaluate hypothesis 3c (factors associated with the composite primary endpoint of on therapy and adherence > 90%), multivariable logistic regression models will also be used. A subgroup analysis by treatment arm will be conducted, looking at each arm separately. Descriptive analysis will be performed within each subgroup

to compare adherent versus non-adherent subjects. The models will include the following potential covariates: demographics, ongoing substance use, untreated mental illness, socioeconomic status, HIV risk transmission behaviors, low health/ HIV and system literacy, fear of disclosure and non-English. Further, any covariates (including stratification factors) that are simultaneously unbalanced at baseline (univariate $p < 0.10$) and associated with the outcome (univariate $p < 0.15$) will be included in the model as observed confounders. Sub-group analyses based on race/ ethnicity, gender, primary language, socioeconomic status by randomization arm will also be conducted. Secondary endpoints for adherence will be analyzed analogously to the primary endpoint.

- 9.6.5 Safety and tolerability of daily TDF/FTC given for PrEP including discontinuation for any adverse event, serious adverse events and adverse events (grade 2 or higher) will be compared between study arms. Descriptive statistics will be used to characterize safety events. Fisher's exact test will be used to compare discontinuation rates due to safety and incidence rates of adverse events and serious adverse events. The time to TDF/ FTC discontinuation for adverse events will be compared between groups using the log-rank test and plotted using Kaplan-Meier curves. Similar analysis will be done for the time to discontinuation for any reason (including drop-out or subject electing to stop PrEP due to lack of perceived risk for HIV).

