1.1.2 Hypothesis II
MSM and transgender M to F having sex with men with high risk of HIV acquisition randomized to the iTAB intervention will have higher adherence to TDF/FTC for PrEP over 48 weeks, as measured by having five of five detectable qualitative FTC plasma concentrations at scheduled visits compared to MSM that have comprehensive standard of care alone.

1.2 Study Secondary Objectives:

1.2.1 To compare adherence to TDF/FTC in the iTAB versus SoC in the subjects that remain on PrEP (at 48 weeks and up to 96 weeks of follow up) by the continuous measure of percent days adherent by the cumulative 4 day ACTG and the visual analog scale (VAS) recall in an 'as treated' analysis.

1.2.2 To compare adherence to TDF/FTC in the iTAB versus SoC groups for the duration of the study (up to 96 weeks). Adherence will be compared using the same outcomes as hypothesis I (self-reported to be on drug and 90% adherent) and II (100% detectable FTC at each scheduled visit) as modified intent to treat analysis.

1.2.3 To determine factors associated with poor adherence/lost to PrEP in study participants (outcomes of < 90% adherent on drug at 48 weeks by ACTG 4 day recall or discontinuation of drug). Factors associated with poor adherence to TDF/FTC will include demographics, ongoing

substance use, untreated mental illness, socioeconomic status, low health/HIV and system literacy, fear of disclosure and non-English language.

- 1.2.4 To determine the factors associated with discontinuation of TDF/FTC at any time point including change in perceived and actual risk of HIV acquisition, demographics, ongoing substance use, untreated mental illness, socioeconomic status, low health/HIV and system literacy, fear of disclosure and non-English language.
- 1.2.5 To determine the rate of HIV seroconversion in PrEP users and compare the iTAB to SOC arms for number of new infections as a proportion at 48 weeks and end of study.
- 1.2.6 To measure acquisition of other sexually transmitted infections (STIs); the proportion of subjects with any new STI at any site will be compared between the iTAB to SOC arms at 48 weeks and through the end of the study.
- 1.2.7 To evaluate changes in risk behavior after initiation of PrEP (risk compensation) comparing baseline to subsequent visits for number of HIV positive/unknown status partners and any unprotected anal intercourse with an HIV positive/ unknown status partner.

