3.0 STUDY DESIGN

3.1 Study Design

CCTG 595 is a comparative, interventional study that uses text messaging to improve adherence of PrEP in MSM and transgender that are at high risk of acquiring HIV. We will conduct an open-label, randomized, controlled clinical trial to evaluate an intervention strategy that uses a developed texting adherence method, the iTAB system, to improve adherence and retention compared to standard of care which will not have iTAB (see study schema). The RCT will occur in the context of implementation of PrEP at three large, diverse, urban HIV care clinics in the CCTG network at UCLA-Harbor, USC and UCSD and a fourth site at the Long Beach Public Health Department. These sites are collaborating with local testing sites to provide an integrated program that identifies individuals at highest risk for HIV acquisition and link them into preventive care that will provide the assessment, dispensing and monitoring of PrEP. A uniform system of HIV testing, risk assessment, health education and behavioral/adherence counseling will be developed for use at consortium sites.

Study enrollment criteria is based on the CDC guidance for PrEP use among MSM and transgender with ongoing risk for HIV infection. All subjects will be confirmed to be uninfected with no contraindication to TDF/FTC. Subjects will be randomized at baseline to iTAB versus SoC. Randomization will be stratified by CCTG site. Study visits will include screening, baseline, week 4 and 12 initial visits and then visits every 12 weeks. Visits for iTAB and SoC arms will both include routine HIV testing and counseling, STI testing, adherence counseling, and medical monitoring. Each visit will include a computer-assisted survey for self-reported adherence assessment and risk behaviors. Drug level monitoring will be performed for FTC qualitative levels in retrospect on banked samples and additional banked specimens will be available for future use and TDF measurement. Adherence by self-reported measures and FTC levels will be used for the main and secondary analyses of the study. Additional outcomes for the study will include changes in risk behavior and determinants of PrEP adherence. Outcomes will be assessed at 48 weeks and for the cumulative follow up of all participants. The study will continue for 48 weeks after randomization of the last participant (up to 96 weeks for any subject).

In order to have adequate representation of African Americans in the study population,

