enrollment of non-African Americans will be capped at 85% of 400 subjects (340) to achieve at least 15% African Americans. If 340 non-African American subjects are enrolled, then enrollment for this subgroup will stop and the study will remain open only for African Americans.

3.2 iTAB Adherence Intervention

This proposal will perform a study of potential methods to improve adherence and retention by evaluating standard procedures versus the use of the iTAB platform. All subjects will receive SoC that will include health education, clinical assessments, laboratory safety monitoring, STI and HIV screening, HIV risk reduction counseling, assessment of psycho-social barriers, adherence counseling, and completion of a computer based survey.

Subjects will be randomized to 1) SoC clinic visits as outlined in section 6.0 and 2) SoC visits plus support using text messaging through the iTAB system. Subjects assigned to the iTAB intervention will have visits with the study coordinator to introduce the iTAB texting system, discuss contact information to assist in recovering the subject if they miss appointments and provide training on iTAB framework for texting supportive reminder messages and tracking adherence. The study will provide subject reimbursement to pay for unlimited text message use and in cases where a subject does not have a phone, the appropriate cell phone will be provided.

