8.0 CRITERIA FOR TREATMENT DISCONTINUATION

8.1 Criteria for Discontinuation from Study

- 8.1.1 Diagnosis of HIV infection.
- 8.1.2 Request by the subject to withdraw.
- 8.1.3 Request of the primary care provider if s/he thinks the study is no longer in the best interest of the subject.
- 8.1.4 Clinical reasons believed life threatening by the study physician, even if not addressed in the toxicity management of the protocol, and can no longer continue in follow up.
- 8.1.5 Subject judged by the investigator to be at significant risk of failing to

comply with the provisions of the protocol as to cause harm to self or seriously interfere with the validity of the study results.

- 8.1.6 At the discretion of the CCTG, FDA, CHRP or pharmaceutical sponsors.
- 8.1.7 Misses two consecutive scheduled visits prior to 48 weeks.
- 8.1.8 Misses one scheduled visit after 48 weeks.

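### STI and adverse-event incidence rates are compared with Fisher's exact test on subjects, which ignores time at risk, although iTAB is meant to improve retention

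*Combined protocol and SAP*

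**What the plan says.** Section 9.6.4 states: "The incidence rate of STI will be compared between SOC and ALERT- iTAB intervention arms using Fisher's exact test". HIV seroconversion is handled the same way. Section 9.6.5 applies Fisher's test to "incidence rates of adverse events and serious adverse events". Objective 1.2.6, by contrast, names the STI outcome as a proportion of subjects, "compared between the iTAB to SOC arms at 48 weeks and through the end of the study".

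The only time-to-event analyses planned concern stopping drug: "The time to TDF/ FTC discontinuation for adverse events will be compared between groups using the log-rank test", with a similar analysis for stopping for any reason (9.6.5). The default population is every randomized subject dispensed drug (9.6.1). Missing adherence forms and missing FTC results have explicit rules (9.1, 9.6.3). Missing STI tests have none.

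On follow-up:
- It ends 48 weeks after the last enrollment, with a maximum of 96 weeks (Schema).
- Section 3.1 describes iTAB as a method "to improve adherence and retention compared to standard of care which will not have iTAB", and Section 3.2 has the iTAB coordinator "discuss contact information to assist in recovering the subject if they miss appointments".
- Grounds for ending participation include "Misses two consecutive scheduled visits prior to 48 weeks" (8.1.7) and "Misses one scheduled visit after 48 weeks" (8.1.8).
- STI tests are scheduled at week 0, every 24 weeks, at end of study or premature discontinuation, and at interim and suspected-infection visits (6.1).
- Subjects who stop drug but stay on study are still STI-tested, while creatinine and dipstick monitoring stop (6.4).

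**The concern.** A proportion of subjects with an event, counted through a variable end of follow-up, depends on how long each subject is observed. Randomization balances entry dates, so staggered enrollment alone does no harm. It does not balance drop-out after randomization, and retention is something this intervention is meant to change. If iTAB subjects stay on study longer, more of their infections and adverse events are found.

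At stake is a false signal that iTAB raises STI or adverse-event risk, or a real reduction that goes unseen. In a PrEP trial that also studies risk compensation (1.2.7), such a signal would be easy to misread.

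**Working it through.** **The plan's own figures.** No power or error figure is given for STIs or adverse events. The one figure available for a between-arm test is the power in Section 9.4 (200 per arm, two-sided alpha 0.05). Full enumeration of Fisher's test gives 94.0% for 30% vs 15% (stated 94%) and 84.5% for 30% vs 17% (stated 84%), so the Fisher calculation used here agrees with the plan's.

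**Closed-form check.** Take a first-event rate L equal in both arms and a constant drop-out hazard d. The chance of a detected event by time T is L/(L+d) × (1 − exp(−(L+d)T)). Both L and drop-out are assumptions. Take L = 0.5 per year, T = 48/52 = 0.923 years, and an illustrative week-48 drop-out of 30% (SoC) vs 15% (iTAB):
- SoC: d = −ln(0.70)/0.923 = 0.386; 0.5/0.886 × (1 − exp(−0.818)) = 0.315.
- iTAB: d = −ln(0.85)/0.923 = 0.176; 0.5/0.676 × (1 − exp(−0.624)) = 0.343.
- Excess at week 48: (0.343 − 0.315) × 200 = 5.6 subjects. Fisher rejects in 7.5% of trials.
- Averaged over follow-up uniform on 48-96 weeks: 0.394 vs 0.445, about 10 extra subjects. Fisher rejects in 14.9%, almost always with iTAB looking worse. Expected person-years are 213 vs 245.

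In simulations of this model with the same drop-out and L of 0.2, 0.5 and 0.9, a person-time comparison rejects in 4.8-5.1% at both time points.

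**Simulation on the visit schedule.** All inputs are assumptions: equal STI hazards of 0.4-0.8 per year; 200 per arm in four equal sites with hazard multipliers 0.7-1.3; detection at weeks 24, 48, 72, 96 and end of study; and 0%, 50% or 100% of drop-outs tested on leaving.

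| Week-48 retention, SoC vs iTAB | Excess iTAB subjects with STI, end of study | Fisher false positives, end of study | Fisher false positives, week 48 |
|---|---|---|---|
| 77.5% both | none expected | 3.3-3.8% | – |
| 80% vs 85% | 1.6-2.8 points | 4.6-6.9% | 3.9-5.3% |
| 85% vs 92.5% | 2.1-4.3 points | 5.7-11.3% | 3.8-6.9% |
| 70% vs 85% | 4.4-8.4 points | 12.8-34.4% | 7.1-16.7% |

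- Repeating the end-of-study settings with exact Fisher enumeration gave 4.8-7.2%, 5.7-11.2% and 12.8-35.6% for the three gaps. A further run gave about 4-8%, 5-10% and 14-38%.
- If drop-out doubles after week 48, the ranges are 4.2-6.5%, 4.9-13.9% and 12.5-40.0%.
- The site-stratified log-rank test stays at 4.0-7.8% across all these STI settings, and the week-48 Kaplan-Meier difference at 3.8-6.3%.
- With a hypothetical 30% lower STI hazard on iTAB and 80% vs 85% retention, power is 28-46% for Fisher and 49-75% for log-rank. With equal retention it is 40-58% and 48-70%, so part of the gain is ordinary time-to-event efficiency.

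**Adverse events** at 0.1-0.6 per year, same three gaps: Fisher 3.2-5.9%, 3.9-7.1% and 5.1-21.3%; log-rank 4.3-6.3%.

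**Safety-laboratory events.** Here observation ends with drug. With 95% study retention in both arms and the same three gaps in being on drug at week 48, Fisher gives 3.2-6.1%, 3.8-8.3% and 6.7-22.9%. Log-rank censored at the last study visit reaches 22.0%; censored at the last on-drug laboratory assessment it is 4.0-5.5%.

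**Rare events.** At 0.05 per year with 30% vs 15% drop-out, the excess at end of study is 1.5 subjects and Fisher rejects in 3.9%. For HIV at 1 per 100 person-years it rejects in 0.7%.

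**The case against.** The best defence is that this is mostly wording. Objective 1.2.6 defines a proportion, Fisher's test suits a proportion, and the protocol uses rate loosely elsewhere (9.4, 9.6.2). On this view 9.6.4 needs one word changed. The inconsistency is real, but changing the word leaves the problem: a through-end-of-study proportion still depends on time observed.

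Second, no text says that drop-outs count as event-free, and Section 9.0 leaves detail to a SAP that takes precedence. Fisher's test on study completers gave 3.3-4.4% false positives in every setting. But that discards randomized subjects, against the default in 9.6.1, and relies on non-informative drop-out.

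Third, testing at premature discontinuation is scheduled. With every drop-out tested, false positives were 4.3-5.5%, 4.1-6.3% and 13-22% for the three gaps. STI history is also taken at every visit, including tests done elsewhere (6.2.3, 6.3.7). Adding detection at the remaining scheduled visits lowered the worst case from 37% to 28%. This objection stands, and it is why the upper figures should not be read as expected values.

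Fourth, discontinuation is compared by arm (9.6.2, 9.6.5). That would reveal a retention gap but would not correct these comparisons.

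**Conclusion.** The point holds in conditional form. If iTAB improves study retention appreciably, Fisher's test on subjects tilts the STI and adverse-event comparisons against iTAB when true rates are equal, mainly through end of study. For STIs under the stated assumptions, the false-positive rate is about 4-8% at a 5-point gap, 5-11% at 7.5 points and 13-38% at 15 points. Faster drop-out after week 48 would raise the upper ends. Week 48 is affected less. The outcomes are secondary and the primary conclusion is untouched, so the weight is low to moderate.

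A reader might infer more than the documents support:
- *That the trial expects 30% vs 15% attrition.* Those figures in 9.4 are rates of the composite endpoint, which also covers visits out of window, low self-reported adherence and stopping drug (9.1). Even read as failures, they cap loss within each arm and do not bound the gap between arms; 30% vs 0% would also fit. The 15-point gap is only an illustration.
- *That SAE and HIV comparisons are distorted.* Section 11.4 does not expect SAEs, Section 9.6.4 expects few new HIV infections, and events this rare show no material inflation.
- *That laboratory toxicity is the same problem.* Its observation ends with drug (6.4), not with study participation, so it needs its own censoring rule.

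**What to change.** In the SAP:
1. Make the through-end-of-study STI comparison a site-stratified log-rank test of time to first new STI. Time events by nominal scheduled visit, and censor at the last scheduled, interim or discontinuation visit with STI testing. State how tests between visits map to nominal visits.
2. At week 48, compare Kaplan-Meier estimates on nominal visits, so that tests within the ±14-day window count as week 48. On actual dates late tests would be lost: at 0.6 per year with uniform timing, the estimate is 33.2% against 42.7% detected by that visit. Report raw proportions descriptively.
3. Analyse time to first grade 2 or higher adverse event the same way, by visit interval. Censor safety-laboratory events at the last on-drug laboratory assessment.
4. Leave SAE and HIV comparisons on Fisher's test.
5. Use one term for the STI outcome in 1.2.6 and 9.6.4.

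The cost is wording in a SAP that Section 9.0 says is finalized before database lock. Log-rank and Kaplan-Meier are already planned in 9.6.5, and no new data are needed. The drawbacks are modest:
- The CRF places adverse events only within a visit interval (6.3.6).
- Subjects with no post-baseline test contribute nothing.
- Informative drop-out can leave some bias. Log-rank false positives were 4.7-5.8% when higher-risk subjects left more (Fisher 4.8-25.3%) and 4.3-8.2% when lower-risk subjects did (Fisher 4.5-14.1%).

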Study Population: Eligible subjects will include HIV-uninfected men who have sex with men (MSM) and male to female (M to F) transgender individuals who have sex with men at least 18 years of age and who have a recent history of high-risk transmission behavior.

Stratification: The randomization will be stratified based on clinic site.

Intervention: All subjects will start PrEP with TDF + FTC fixed dose combination given once daily. Subjects will be randomized (1:1) to either the iTAB text messaging adherence reminder intervention with SoC or the SoC alone arm. Subjects placed into the iTAB intervention arm will receive a personalized, automated texting system to maintain adherence and retention. Both groups will receive access to PrEP in accordance with standardized comprehensive methods of prescribing, risk reduction counseling, adherence counseling, and clinical assessments that include safety monitoring, as well as HIV and STD screening.

Regimen: TDF 300 mg + FTC 200 mg fixed dose combination will be given orally once daily starting at the baseline visit (month 0) and continued throughout the study.

Outcomes: The CCTG 595 primary outcome is defined as a composite endpoint of remaining on PrEP and having adherence > 90% over 48 weeks of follow-up. The adherence endpoint will be derived from the 4 day ACTG adherence assessment from each of the visits from week 4, 12, 24, 36, and 48. 'Adherent' will be defined as self-reported TDF/ FTC adherence of 90% or greater (at least 18 of 20 days). If a subject misses an adherence assessment within the window of a scheduled visit or discontinues study prior to week 48, then the missed visits will be counted no adherence for the time of that visit. All randomized subjects that were dispensed PrEP at baseline will be included in the modified intent-to-treat analysis.

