9.1 Primary Endpoints

Adherent to PrEP through 48 weeks is defined as a composite endpoint of continuing on study (made all scheduled visits within window in the 48 week period) and on study medication and greater than or equal to 90% adherent to medication defined by self-report of ≥ 18 of 20 doses of medication on the 5 ACTG adherence questionnaires at weeks 4, 12, 24, 36 and 48. Missing adherence forms will be imputed as no doses taken.

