9.2 Secondary Endpoints

- 9.2.1 Adherent to PrEP by FTC measurement at 48 weeks and at the end of study follow-up is defined by attending all scheduled visits and having detectable FTC.
- 9.2.2 Adherent to PrEP in continuous follow up is aggregate percentage of self-reported ACTG days of adherence where missed schedule visits are counted as 0/4 days.
- 9.2.3 Poor adherence is considered those with <90% self-reported adherence by ACTG 4 day survey or if discontinued drug. Subgroup analysis should explore the endpoint for discontinuation for reasons other than quit drug for lack of risk or confirmed adverse event.
- 9.2.4 Safety and tolerability defined as: i) discontinuation of TDF/ FTC for any

toxicity; ii) grade 2 or higher adverse event or laboratory toxicity; iii) serious adverse event; iv) death

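### The poor-adherence factor analysis has one outcome in 1.2.3 and 9.2.3 and another in 9.6.4, where the primary composite adds a visit-window condition and a stricter threshold

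*Combined protocol and SAP*

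**What the plan says.** Three sections bear on the outcome of this analysis, and a fourth supplies a definition.

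- Section 1.2.3, the objective on factors for poor adherence or loss to PrEP: "outcomes of < 90% adherent on drug at 48 weeks by ACTG 4 day recall or discontinuation of drug".
- Section 9.2.3, the matching endpoint: "Poor adherence is considered those with <90% self-reported adherence by ACTG 4 day survey or if discontinued drug". It gives no time point.
- Section 9.6.4, the analysis: logistic regression for "factors associated with the composite primary endpoint of on therapy and adherence > 90" per cent. It ties this to a hypothesis 3c, which section 1 does not contain.
- Section 9.1, the primary composite: "continuing on study (made all scheduled visits within window in the 48 week period) and on study medication". Its dose requirement is a threshold of 90% or more, met by reporting 18 or more of the 20 doses covered by the recalls at weeks 4, 12, 24, 36 and 48.

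On missing data, 9.1 says "Missing adherence forms will be imputed as no doses taken". The Schema gives no adherence credit for a visit "If a subject misses an adherence assessment within the window of a scheduled visit or discontinues study prior to week 48". Section 9.2.2 counts a missed scheduled visit as 0/4 days; 9.2.3 has no such rule. Section 9.6.4 closes by saying that secondary adherence endpoints are handled in the same way as the primary one, without saying whether that includes the zero rule.

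The schedule in 6.1 sets a ±14-day window and allows an interim visit, with adherence review, after the window has passed.

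**The concern.** The objective asks who takes PrEP poorly or is lost to it. If the model uses the 9.1 composite, its failures also include people on drug who report full dosing but attended one visit out of window. A covariate such as substance use or non-English language could then appear to predict poor adherence when it predicts late attendance. In addition, 9.6.4 names the composite but paraphrases it without the attendance condition and with a strict inequality. An analyst could therefore follow the objective, the full composite or the paraphrase, and each can classify the same subject differently.

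**Working it through.** The plan gives no figure for this analysis. Its only related calculation is the power of the primary comparison in 9.4 (94% for 30% v 15%, 84% for 30% v 17%, 200 per arm). Exact Fisher power gives 94.0% and 84.5%, so those figures reproduce; nothing here depends on them.

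The check applies each definition to two subjects, both on drug at week 48.

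**Subject A** reports 4/4 at all five assessments; one visit falls outside ±14 days and is made up at an interim visit. Section 8.1 removes a subject before week 48 only after two consecutive missed visits, so A stays in the study.

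**Subject B** has every visit in window and reports exactly 18 of 20, so 18/20 = 90%.

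| Definition | Subject A | Subject B |
|---|---|---|
| 1.2.3 and 9.2.3 as written (<90% is poor) | 20/20 (late form counted) or 16/16 (late form dropped) = 100%: not poor | 90% is not <90%: not poor |
| 1.2.3 and 9.2.3 with the zero rule carried over | (20 − 4)/20 = 16/20 = 80%: poor | 90%: not poor |
| 9.1 composite (all visits in window, ≥90%) | fails on attendance; the Schema's zero rule also gives 80% | 90% ≥ 90%: adherent |
| 9.6.4 paraphrase alone, no zero rule (>90%) | 100% > 90%: adherent | 90% is not >90%: not adherent |

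The results are:

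1. A is classified differently by 1.2.3/9.2.3 as written and by 9.6.4 read through 9.1. The conflict disappears if the zero rule reaches 9.2.3, or if 9.6.4 means only its paraphrase.
2. B is classified differently by 9.1 and by the threshold in 9.6.4. This needs no missing-data assumption. With 20 recall days the next score is 19/20 = 95%, so the strict sign raises the requirement by one day.

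The documents give no late-visit rate, so any count is illustrative. If each of five visits is independently out of window with probability q, the share of subjects with at least one is 1 − (1 − q)^5:

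- q = 1%: 4.9%, about 20 of 400
- q = 2%: 9.6%, about 38
- q = 5%: 22.6%, about 90
- q = 10%: 41.0%, about 164

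These are ceilings on type-A reclassification, since some of these subjects would be poor adherers under either definition.

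**The case against.** The best defence is that the definitions were meant to be the same. The zero rules in the Schema, 9.1 and 9.2.2, with the closing sentence of 9.6.4, can be read as reaching 9.2.3; A is then non-adherent under both. The strict sign looks like loose shorthand: the Schema and 9.6.2 also use it, and the Schema then defines adherent as 90% or greater. Attendance is also tied to drug access, because supply lasts until the next scheduled visit (5.1.2) and is not renewed after a missed appointment (6.2.3). Finally, section 9.0 requires a SAP before database lock that overrides section 9, and it could settle the matter; no separate SAP text was available here.

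Much of this stands. It makes the case of A conditional, and it supports keeping the composite as a second model. It does not supply the missing statement: 9.2.3 omits a rule that the item before it states, and no passage says whether attendance counts in this analysis.

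A reader might infer more than the documents support:

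- *Three separate outcomes, with 1.2.3 resting on the single week-48 recall.* With independent days, that recall and the 18-of-20 rule would disagree for 11% of subjects at 97% daily adherence and 34% at 85%. But Hypothesis I uses the same week-48 phrasing for the composite that the Schema builds from five assessments, 1.2.1 speaks of a cumulative recall, and a 90% cut has little meaning on four days. Sections 1.2.3 and 9.2.3 differ only in the time point.
- *A takes every dose.* Given the supply rules, the documents support only that A reports every dose at each recall.
- *The outcome is free to be chosen after the data are seen.* The SAP requirement means this cannot be asserted.

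**Conclusion.** The inconsistency is real and worth correcting, but it concerns a secondary analysis. The split is two-way: 1.2.3 and 9.2.3 on one side, 9.6.4 read through 9.1 on the other, with a threshold mismatch inside 9.6.4. The threshold conflict holds on the wording alone. The visit-window conflict holds if 9.6.4 imports the composite it names and the zero rule does not extend to 9.2.3. Neither the number affected nor the effect on the fitted associations can be estimated from the documents; the range shown rests on assumed rates and independent visits.

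**What to change.** Use one outcome in 1.2.3, 9.2.3 and 9.6.4: TDF/FTC discontinued (including loss to follow-up), or fewer than 18 of 20 recall days (<90%) over the week 4 to 48 assessments.

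- Score an assessment never completed as 0/4, in line with 9.1 and 9.2.2.
- Score an assessment completed out of window by its reported doses, so that lateness alone is not poor adherence.
- In 1.2.3 change *at* to *through* 48 weeks. In 9.6.4 change > to ≥ 90%, and correct the reference to hypothesis 3c.
- Fit the same covariates to the full 9.1 composite as a second model.

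Under this rule A (20/20) and B (18/20) are not poor adherers. A subject who never completes one assessment scores 16/20 = 80% and is, as is one lost after week 24 (12/20 = 60%). Keeping all 20 days in the denominator matters because the objective covers loss to PrEP; averaging over attended assessments only would let an early perfect reporter who then disappears count as adherent.

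The cost is wording in three places and one extra model. The main factor-analysis outcome is then no longer exactly the primary composite, and the treatment of late completed assessments departs from the Schema, so the text should say that it applies to this analysis only.
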